4.2.1 Number of subjects required to be included in the study

Approximately 170 subjects will be enrolled in the study.

4.2.2 Estimated time needed to enroll this subject population

4.3 OBJECTIVES

4.3.1 Primary Objective

The primary objective of the study is to demonstrate subject's preference for a stimulation modality.

4.3.2 Secondary Objective

The secondary objective of the study is to demonstrate the safety of the hybrid DBS system.

4.4 ENDPOINTS

4.4.1 Primary Endpoint

The primary endpoint is the proportion of subjects who indicate preference on constant current over constant voltage at the 3 Month follow-up visit.

Clinical Investigational Plan

4.4.2 Secondary Endpoint

The secondary endpoint is the rate of safety events related to battery replacement procedures for hybrid systems.

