3.3 ANTICIPATED ADVERSE EVENTS AND ADVERSE DEVICE EFFECTS

The replacement of a DBS IPG involves risks. In addition to those risks commonly associated with surgery, the following risks are also associated with implantation and / or use of the device:

Intracranial hemorrhage (which can lead to stroke, paralysis or death); subcutaneous hemorrhage or seroma; hematoma; cerebrospinal fluid leakage or cerebrospinal fluid abnormality; brain contusion; infection or inflammation; antibiotic anaphylaxis; skin disorder; edema; persistent pain at surgery site or IPG site; erosion; brachial plexus injury (nerves to chest, shoulder and arm); postoperative pain, stress, or discomfort; neuropathy (nerve degeneration); hemiparesis (muscular weakness or partial paralysis on one side of the body); ballism or hemiballism (uncontrollable movements on both or only one side of the body); confusion – transient, nocturnal or ongoing; cognitive impairment, including delirium, dementia, disorientation, psychosis and speech difficulties; aphasia; deep vein thrombosis; complications from anesthesia; phlebitis (vein inflammation); pulmonary embolism (sudden blood vessel obstruction); aborted procedures (air embolism, unable to find target, surgical complication, etc.); complications from unusual physiological variations in patients, including foreign body rejection phenomena; pneumonia, seizure or convulsions; paralysis (loss of motor function, inability to move); stroke and death.

Complications may occur leading in some cases to surgical revision or explant of the system.

Possible deep brain stimulation complications include, but are not limited to the following:

Device-related complications:

- Undesirable changes in stimulation related to cellular changes in tissue around the electrodes, changes in the electrode position, loose electrical connections, or lead fracture
- Loss of therapeutic benefit due to a change in electrode positions, loose electrical connections, or lead or extension fraction
- Initial jolt or tingling during stimulation; jolting or shocking sensations
- Infection
- Paresthesia
- Lead fracture, migration or dislodgement
- Misplaced lead
- Extension malfunction, fracture or disconnect
- Deep brain stimulation system failure or battery failure with the device
- Deep brain stimulation system malfunction or dislodgement
- Spontaneous turning on or off of the IPG

Clinical Investigational Plan

- Allergic or rejection response to implanted materials

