8.1.5 Serious Adverse Device Effect (SADE)

Adverse device effect that has resulted in any of the consequences characteristic of a serious adverse event.

Clinical Investigational Plan

For **unexpected failure modes** or unexpected adverse events, the site should follow their standard reporting practices for **medical device reporting (MDR)/ Vigilance reporting** for medical devices per the regulations.

8.2 PROCEDURE FOR ASSESSING, RECORDING, AND REPORTING ADVERSE EVENTS, DEVICE DEFICIENCIES/COMPLAINTS, ADVERSE DEVICE EFFECTS, SERIOUS ADVERSE EVENTS, AND SERIOUS ADVERSE DEVICE EFFECTS:

Safety surveillance within this study and the safety reporting both performed by the investigator, starts as soon as the subject is enrolled in this study (date of signature of the informed consent). The safety surveillance and the safety reporting will continue until the last investigational visit has been performed, the subject is deceased, the subject/investigator concludes his participation into the study or the subject/investigator withdraws the subject from the study, except as otherwise specified in the CIP.

Adverse event data as well as deaths will be collected throughout the clinical study and will be reported to the Sponsor through the EDC system. The Investigator will record adverse events on the appropriate case report forms.

Records relating to the subject's subsequent medical course must be maintained and submitted (as applicable) to the Sponsor until the event has subsided or, in case of permanent impairment, until the event stabilizes and the overall clinical outcome has been ascertained. Adverse events will be monitored until they are adequately resolved. The status of the subject's condition should be documented at each visit.

The investigator will report the event to the IRB/EC per their reporting requirements.

For this study, reportable events to sponsor are considered:

All procedure or device related Adverse Events (whether or not the event is considered serious).

- ADEs (procedure/device related)
- SADEs (procedure/device related)

These events will be reported to the Sponsor, as soon as possible in accordance to the local laws and regulations.

The Sponsor will ensure that all events are reported to the relevant authorities as per regulations.

Additional information may be requested, when required, by the Sponsor in order to support the reporting of AEs to regulatory authorities.

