12.1.1 Primary Endpoint

12.1.2 Secondary Endpoint

The rate of safety events related to battery replacement procedures for hybrid systems.

Clinical Investigational Plan

The event rate will be summarized as (1) # events per patient-year of follow up and (2) incidence rate. The number of events per patient-year of follow-up will be calculated as the total number of safety events related to battery replacement procedures for hybrid systems divided by total follow-up duration from IPG replacement visit to either 12M visit or withdrawal visit (patient-years). The incidence rate (%) will be calculated as number of subjects who undergo IPG replacement and encounter safety events related to battery replacement procedure for hybrid system divided by total subjects who undergo IPG replacement.

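### The secondary objective is the safety of the hybrid DBS system, but the endpoint and both planned statistics count only replacement-procedure events

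*Combined protocol and SAP*

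**What the plan says.** Section 4.3.2 and the synopsis set the objective: "The secondary objective of the study is to demonstrate the safety of the hybrid DBS system". Section 4.4.2 and the synopsis set the endpoint: "The secondary endpoint is the rate of safety events related to battery replacement procedures for hybrid systems".

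Section 12.1.2 plans two summaries. The first is the number of such events divided by patient-years from IPG replacement to the 12-month or withdrawal visit. The second is the number of replaced subjects who "encounter safety events related to battery replacement procedure for hybrid system divided by total subjects who undergo IPG replacement". Both numerators are tied to the replacement procedure.

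Event collection is wider. Section 8.2 makes the following reportable to the sponsor: "All procedure or device related Adverse Events (whether or not the event is considered serious". On duration it says: "The safety surveillance and the safety reporting will continue until the last investigational visit has been performed". Section 8.1.4 defines an ADE by its relation to use of the device and includes malfunction. Table 1 schedules (S)ADE collection at replacement, 3 months and 12 months.

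The descriptive endpoints in 4.4.3 and 12.1.3 cover rating scales, levodopa, satisfaction, preference and health economics. None is a safety summary.

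**The concern.** A hybrid system joins a new IPG to another manufacturer's extensions and leads. The harms that bear on whether that combination is safe include those that appear after surgery and come from the device. Section 3.3 lists examples among its device-related complications: "Deep brain stimulation system failure or battery failure with the device" and "Spontaneous turning on or off of the IPG". An adverse event from such a cause months after replacement may well be judged device-related and not procedure-related.

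If 12.1.2 is followed as written, that event is in neither numerator, and no other planned table would show it. The report would then offer a replacement-procedure rate in answer to a question about system safety. Surveillance is not affected, because these events still go to the sponsor and, as applicable, to the EC/IRB and authorities. The gap is in the planned result.

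**Working it through.** The documents state no safety rate, margin or sample size for this endpoint, so there is no figure of the plan's own to reproduce. The check is a comparison of sections, followed by the effect of one omitted case.

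**Which events are counted**

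| Event judged related to | Reportable (8.2) | Counted in 12.1.2 as written |
|---|---|---|
| Procedure only | Yes | Yes |
| Procedure and device | Yes | Yes |
| Device only | Yes | No |

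Sections 4.4.3 and 12.1.3 do not cover the third row. Section 12.5 assigns reported data to the endpoints they are relevant to, so it creates no further analysis. Section 8.4 gives device deficiencies no dedicated CRF, so apart from the death and withdrawal forms, the ADE/SADE reports are the CRF record of harm from the device.

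**Inputs for the effect per case**

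- Targets in 12.2: 170 enrolled and 115 in the primary analysis. Consent precedes replacement, and the 3-month preference follows it. If both targets are met, between 115 and 170 subjects are replaced.
- The 12-month visit has a window of ±30 days. Taking 12 months as 365.25 days, follow-up is 335.25 to 395.25 days.

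**Incidence.** A subject whose only event is device-related and not procedure-related is missing from the numerator:

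- 1/115 = 0.87 percentage points
- 1/170 = 0.59 percentage points

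A subject who also has a procedure-related event is already counted, so the incidence does not change for that subject. The event rate still misses the device-only event.

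**Event rate.** If every replaced subject is followed to a 12-month visit inside the window:

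- Fewest patient-years: 115 × 335.25/365.25 = 105.6, so one event is 100/105.6 = 0.95 per 100 patient-years.
- Most patient-years: 170 × 395.25/365.25 = 184.0, so one event is 100/184.0 = 0.54 per 100 patient-years.

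At exactly 12 months the figures are 0.87 (115 subjects) and 0.59 (170 subjects).

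**Chance that the gap arises.** The documents give no rate, so let q be the assumed proportion of subjects with at least one device-only event. The chance of one or more such subjects is 1 − (1 − q)^n:

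| Assumed q | n = 115 | n = 170 |
|---|---|---|
| 2% | 90% | 97% |
| 5% | 99.7% | 99.98% |

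This is an illustration only and says nothing about the true rate.

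**The case against.** The best defence is that the endpoint term is undefined and the authors may have meant it broadly. Section 8.2 lists ADEs as procedure/device related in one class. The ADE definition itself takes in implantation and installation. Section 3.4, although headed as device risk, speaks of procedural risks of replacing one device with another. Person-time runs to 12 months, which suits late events too. This makes a wider intention plausible. It does not change what 12.1.2 counts: 8.2 names procedure and device separately for reporting, while 12.1.2 names only the replacement procedure. Even on the lenient view, two analysts could produce different safety rates from the same data, and that also needs correction.

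Several narrower points stand:

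- Section 12.5 is not independent proof, because which events are relevant depends on how the endpoint is read.
- A malfunction without harm is a device deficiency and goes to product surveillance (8.4). No change to this endpoint would capture it. The concern is confined to adverse events.
- Whether sites record procedure and device relatedness separately depends on CRFs that are not part of the document (Appendix G).
- The per-case figures follow from the sample size alone and do not show how many events would be lost. Withdrawals would shorten follow-up, so 0.95 per 100 patient-years is not an upper limit.
- Section 12.1.2 describes summary rates with no test or threshold, and reporting to the sponsor is intact. This limits the severity but does not close the gap between objective and endpoint.

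**Conclusion.** The concern holds. The synopsis, 4.4.2 and both numerators in 12.1.2 agree on a procedure-only count, the objective is system-wide, and nothing else in the planned analysis covers device-only events. The only planned safety result therefore cannot support the stated objective and could understate system-related harm over the 12 months.

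The total understatement cannot be given. The per-case effect of 0.87 to 0.59 percentage points in incidence assumes that the targets are met and that 115 to 170 subjects are replaced. The effect of 0.95 to 0.54 per 100 patient-years also assumes full follow-up to a 12-month visit inside its window. The mismatch in the text is clear. What remains uncertain is whether a wider count was intended and how many events it would add. The point should be corrected, but it does not touch the primary endpoint or the surveillance of subjects.

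**What to change.** Either of two changes resolves it.

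1. **Widen the endpoint.** In 4.4.2, the synopsis and 12.1.2, define the secondary endpoint as all procedure- or device-related ADEs and SADEs from IPG replacement to the 12-month or withdrawal visit, over all subjects who undergo replacement. Show the procedure-related subset separately where the CRF records relatedness. The 8.2 exclusions stay, so events tied to programming sessions remain outside the result, and the report should say so. The cost is revised wording and one extra table, using events already reportable through EDC. The reported rate may be higher.
2. **Narrow the objective.** In 4.3.2 and the synopsis, limit the objective and the conclusion to safety of the replacement procedure, which fits the framing in 3.4, and define which events count as procedure-related. The cost is that the study draws no conclusion on system safety.

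Two optional clarifications could go in at the same time. One is a 95% confidence interval for the incidence: with no event observed, the exact two-sided upper limit, 1 − 0.025^(1/n), is 3.16% for 0/115 and 2.15% for 0/170. The other is a sentence that the denominator in 12.1.2, not the complete-data rule in 12.6, governs the safety analysis.

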4.4.3 Descriptive Endpoints

The following data will be collected:

- The change in Speech Handicap Index at 3 and 12 Months compared to Baseline;
- The change in total UPDRS score and the individual UPDRS components at 3 and 12 Months compared to Baseline;
- The change in Levodopa medication at 3 and 12 Months compared to Baseline;
- The change in FOGQ scores at 3 and 12 Months compared to Baseline;
- The change in Tinetti Test scores at 3 and 12 Months compared to Baseline;
- The change in Berg Balance Scale scores at 3 and 12 Months compared to Baseline;
- The change in PDQ-39 scores at 3 and 12 Months compared to Baseline;
- Proportion of subjects who indicate satisfaction with constant current at 3 and 12 Months;
- Proportion of caregivers who indicate satisfaction with constant current at 3 and 12 Months;
- Proportion of subjects who indicate preference on constant current over constant voltage at 12 Months;
- Summary of Health Economic Data between constant current and constant voltage.

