Note: If a subject misses one or more of the scheduled follow up visits (inclusive of the assigned visit windows), this will be considered as a missed visit. The subject may therefore still return for subsequent visits and will not be excluded from the study.

If a subject withdraws from the clinical study, the site will record the subject's reasons for withdrawal, on a Withdrawal CRF.

When subject withdrawal from the clinical study is due to an adverse event the subject will be followed until resolution of that adverse event or determination that the subject's condition is stable. The status of the subject's condition should be documented at the time of withdrawal.

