12.1.3 Descriptive Endpoints

The following descriptive endpoints will be reported:

- The change in Speech Handicap Index at 3 and 12 Months compared to Baseline;
- The change in total UPDRS score and the individual UPDRS components at 3 and 12 Months compared to Baseline;
- The change in Levodopa medication at 3 and 12 Months compared to Baseline;
- The change in FOGQ scores at 3 and 12 Months compared to Baseline;
- The change in Tinetti Test scores at 3 and 12 Months compared to Baseline;
- The change in Berg Balance Scale scores at 3 and 12 Months compared to Baseline;
- The change in PDQ-39 Quality of Life scores 3 and 12 Months compared to Baseline;
- Proportion of subjects who indicate satisfaction with constant current at 3 and 12 Months;
- Proportion of caregivers who indicate satisfaction with constant current at 3 and 12 Months;
- Proportion of subjects who indicate preference on constant current over constant voltage at the 12 Month follow-up visit.
- Summary of Health Economic Data for constant current compared to constant voltage.

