12.2 SAMPLE SIZE

The target number of subjects for enrollment is 170 and the target number of subjects for the primary endpoint analysis is 115.

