12.5 PROCEDURES THAT TAKE INTO ACCOUNT ALL THE DATA

All reported data will be used in the analysis for relevant endpoints. Missing data will be excluded from the respective endpoint analysis.

Clinical Investigational Plan

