12.6 THE TREATMENT OF MISSING, UNUSED, OR SPURIOUS DATA, INCLUDING DROP-OUTS AND WITHDRAWALS

Analyses of each endpoint will be performed in subjects who provide complete data for each endpoint. Subject accountability for enrolled subjects will be performed prior to analyses of the primary and secondary endpoints. There are no plans to perform imputations for missing data, subject dropouts or withdrawals. If spurious data are discovered, these data will be excluded from analyses. Reasons for exclusion of any data from analyses will be summarized.

12.7 THE EXCLUSION OF PARTICULAR INFORMATION FOR THE TESTING OF THE HYPOTHESIS, if relevant

There is no intent to exclude particular information for the testing of hypotheses.

12.8 IN MULTI-CENTER STUDIES, THE MINIMUM AND MAXIMUM NUMBER OF SUBJECTS TO BE INCLUDED FOR EACH CENTER

Each participating will enroll at least one subject to a maximum of 30 subjects.

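### The 12-month change scores rest on 12-month attenders only and ignore the recorded 3-month scores of those who left, and section 12.6 does not define an endpoint by visit

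*Combined protocol and SAP*

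**What the plan says.** Sections 4.4.3 and 12.1.3 list seven change scores: Speech Handicap Index (SHI), UPDRS (total and components), levodopa medication, FOGQ, Tinetti, Berg and PDQ-39. Each is one line naming both follow-up visits, as in "The change in Speech Handicap Index at 3 and 12 Months compared to Baseline". Section 12.1.3 introduces them with "The following descriptive endpoints will be reported". No hypothesis, model, standard deviation or effect size is given for them.

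The missing-data rule is in section 12.6: "Analyses of each endpoint will be performed in subjects who provide complete data for each endpoint". It adds: "There are no plans to perform imputations for missing data, subject dropouts or withdrawals". Section 12.6 also promises subject accountability and a summary of the reasons for leaving out any data.

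Section 12.5 says "All reported data will be used in the analysis for relevant endpoints" and "Missing data will be excluded from the respective endpoint analysis". Section 6.12 treats a missed visit as no reason for removal: "The subject may therefore still return for subsequent visits and will not be excluded from the study".

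The visible text describes no analysis in which a 3-month score informs the 12-month mean. It describes no missing-data sensitivity analysis and no comparison of completers with non-completers.

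**The concern.** There are two separate issues.

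1. **Selection at 12 months.** Whether the rule is applied by line or by visit, a subject seen at 3 months but not at 12 contributes nothing to the 12-month mean, although the 3-month score is on file. The mean is unbiased only if leaving is unrelated to outcome. If leaving is related to the 3-month result, part of the reported 12-month change reflects who came back. A reader who sets the 3-month and 12-month means side by side would also be comparing different groups of subjects.

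2. **What counts as an endpoint.** Section 12.6 does not say whether the endpoint is the whole line or each visit within it. On the whole-line reading, a valid 3-month score is lost when the 12-month visit is missed, and the reverse. Two analysts could then produce different 3-month tables from the same data. The ambiguity has a practical trigger. The visit list in section 6.7 omits SHI at 12 months, while the synopsis, Table 1 and section 6.2 collect it then. These places need reconciling whichever reading is intended.

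Speech and gait are central to the rationale in section 2.0, and section 16.0 commits to submitting the results for publication. The change scores are therefore likely to be read, even though they are not tested.

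**Working it through.** **The plan's own figures.** Section 12.2 says: "The target number of subjects for enrollment is 170 and the target number of subjects for the primary endpoint analysis is 115". This gives 1 − 115/170 = 32.4% of enrolled subjects not contributing to the primary analysis. The rate is back-calculated and concerns loss before the 3-month analysis. No figure is given for loss between 3 and 12 months, or for the SD or correlation of any change score, so those inputs are assumed below.

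**Assumptions.**
- 115 subjects have 3-month scores (borrowed from the primary-analysis target).
- The 3-month and 12-month changes are bivariate normal in SD units, with correlation 0.4, 0.6 or 0.8, and higher is better.
- Leaving before 12 months follows a logistic model in the 3-month change, with overall loss of 10, 15 or 25%.
- The slope is 1 per SD (odds ratio about 2.7, worse subjects leaving more) in the table, and is then varied.

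**Formula.** Bias of the complete-case mean = (fraction lost) × (completer mean − non-completer mean).

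**Simulated bias of the 12-month mean, slope 1 (4,000 runs per setting, SD units):**

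| Loss after 3 months | Correlation 0.4 | 0.6 | 0.8 |
|---|---|---|---|
| 10% | 0.034 | 0.056 | 0.074 |
| 15% | 0.056 | 0.080 | 0.107 |
| 25% | 0.089 | 0.130 | 0.169 |

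**Hand check of the central case.** At 15% loss the completers' 3-month mean is shifted by 0.13 SD. This corresponds to a completer versus leaver gap of 0.13/0.15 = 0.87 SD at 3 months. At correlation 0.6 the 12-month shift is 0.6 × 0.13 = 0.078 SD, which matches 0.080. The standard error is 1/√(115 × 0.85) = 1/√97.75 = 0.10 SD, so the bias is about 0.8 of a standard error.

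**Varying the slope at 15% loss, correlation 0.4 to 0.8:**
- slope 0.5: about 0.03 to 0.06 SD
- slope 0.25: about 0.015 to 0.03 SD
- slope 0: none
- slope −0.5 (better subjects leave more): −0.03 to −0.06 SD

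**What a likelihood estimate does.** Using the 3-month score, the estimate stays within about 0.005 SD of the truth in the table's settings, and its standard error is no larger. That follows from letting dropout depend only on the observed 3-month score. If leaving depends instead on the unobserved 12-month status (slope 1, 15% loss), the likelihood estimate is still off by about 0.05 to 0.12 SD, against 0.13 SD for complete cases.

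**Whole-line reading only.** A 15% later loss would discard 0.15 × 115 ≈ 17 valid 3-month scores and shift the 3-month mean by 0.13 SD at slope 1. With visit-wise data, later dropout has no effect on the 3-month mean.

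**The case against.** The strongest reply is that these scores are descriptive and untested. All changes are measured against Baseline, no 3-to-12-month contrast is planned, and observed-case summaries are ordinary practice in a post-market study. The plan also promises an account of exclusions. This stands, and it sets the weight of the point.

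Two stronger readings are tempting, and the documents do not support either:
- **That the plan throws away 3-month results when the 12-month visit is lost.** No section says so. Section 12.5 points the other way, and naming two visits in one line is common shorthand for two summaries. What stands is that 12.6 permits the reading and should be closed off.
- **That the 12-month mean drifts toward those who did well.** Section 6.12 lists lead or extension revision, refusal, ineligibility, death, non-compliance, investigator decision and loss to follow-up. Some of these may relate to a subject's condition, but poor response is not named, and several would fall before 3 months. The bias may be zero or reversed. For levodopa change, the plan does not define which direction is favourable.

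It is also fair to say that the near-zero bias of the likelihood estimate is partly built into the simulation, and that such a model implicitly projects scores for subjects who died. Both are limits of the remedy. Neither favours the complete-case mean, which was further from the truth under both dropout mechanisms.

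**Conclusion.** The point holds in a limited form. Section 12.6 states a rule under which the 12-month mean changes rest on attenders and leave recorded 3-month scores unused. Under assumed loss of 10 to 25%, correlation 0.4 to 0.8 and slope 0 to 1 per SD, the bias is between 0 and about 0.17 SD. In the central case (15%, 0.6, slope 1) it is 0.08 SD, less than one standard error. The sign reverses if subjects doing better are the ones who leave. None of these inputs comes from the plan, and the 32.4% implied by section 12.2 must not be taken as loss after 3 months.

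Separately, the wording of 12.6 is ambiguous and, on one reading, conflicts with 12.5. Severity is low. The primary preference proportion is not affected by this point.

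**What to change.** 1. In 12.6, define each endpoint by visit and state that 3-month data are used whatever happens at 12 months. Word the lines in 4.4.3 and 12.1.3 to match. The same sentence would settle the two satisfaction lines, which are also written for both visits.
2. For the continuous scores, estimate the mean change at each visit with a 95% confidence interval from a repeated-measures likelihood model. Use Baseline, 3-month and 12-month scores as outcomes, visit as a factor and an unstructured covariance, in all subjects who had the IPG replaced and have at least one score.
3. Show the observed-case means and the number of subjects at each visit alongside, with deaths counted separately.
4. Reconcile section 6.7 with the synopsis, Table 1 and section 6.2 on the 12-month SHI.

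The cost is some wording and one standard model per score, on data the plan already intends to collect. The model assumes that scores are missing at random given those observed. That is weaker than what the complete-case mean needs, but bias is reduced rather than removed if leaving depends on unobserved 12-month status.
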